5.4.1 Primary Efficacy Endpoint

The primary efficacy endpoint is:

- The proportion of patients who are able to achieve CDA within 4 weeks (on or prior to Week 5 visit) of starting PRN1008 treatment **without** the need for doses of prednis(ol)one > 0.5 mg/kg

The Control of Disease Activity (CDA) responses are assessed at visits specified in the Schedule of assessments (Table 1). Types of CS other than prednis(ol)one are converted to dose-equivalent prednis(ol)one (see Section 5.4.2.3).

This is operationalized as meaning the first CDA is achieved on or before the Week 5 visit but after first dose of PRN1008, and will be summarized, by dose level to the Week 5 visit and overall in a table, using frequencies and percentages. In addition, two-sided 80% and 95% CIs (Confidence Intervals) of the response rate will be provided for each dose level and overall.

Patients who are able to achieve CDA between first dose of study drug and the Week 5 visit without prednis(ol)one >0.5 mg/kg on the date prior to the CDA will be considered as responders, even if the CDA status was not maintained or higher doses of prednis(ol)one were used after the first CDA. Patients who are not able to achieve CDA prior to or at the Week 5 visit or had prednis(ol)one >0.5 mg/kg on the date prior to CDA will be considered as non-responders. Patients whose CDA status is unknown at the Week 5 visit for whatever reason (including early termination before Week 5 visit) will be also considered as non-responders. Only systemic CSs (as defined by medication taken orally or intravenously) are to be used to evaluate the efficacy endpoints, topical CSs (including buccal CS) will not be counted.

The number and percentage of patients who meet the primary efficacy endpoint criteria will be tabulated by dose level and overall (all patients).

A sensitivity analysis using the Completer and PP population will be provided.

Panel plots will be provided for PDAI score over the study period for each patient. Dose level (mg/day) will also be plotted on the same figure. Lines for the steroid equivalent dose in mg/kg will be added to the plots. A total of 9 plots (3 x 3) will be fitted on one page.

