11.1.2 Efficacy

The proportion of subjects who are able to achieve control of disease activity (CDA) within 4 weeks of starting PRN1008 treatment without the need for doses of prednis(ol)one > 0.5 mg/kg.

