8.1. Primary Efficacy Endpoint

The primary efficacy endpoint is “The proportion of patients who are able to achieve CDA within 4 weeks of starting PRN1008 treatment without the need for doses of prednis(ol)one >0.5 mg/kg at any time”.

Other types of CS are converted to dose-equivalent prednis(ol)one (see Section 8.2.6).

This is operationalized as meaning the first CDA is achieved on or before the Week 5 visit but after first dose of PRN1008, and will be summarized, by maximum dose level to the Week 5 visit and overall in a table, using frequencies and percentages. In addition, two-sided 80% and 95% CIs (Confidence Intervals) of the response rate will be provided for each maximum dose level and overall using the Exact (Clopper-Pearson) method.

Patients who are able to achieve CDA between first dose of study drug and the Week 5 visit and have no occurrence of daily prednis(ol)one >0.5 mg/kg before the date of the first CDA will be considered as responders, even if the CDA status was not maintained or higher doses of prednis(ol)one were used after the first CDA. Patients who are not able to achieve CDA prior to or at the Week 5 visit or have any occurrence of daily prednis(ol)one >0.5 mg/kg before a first CDA during the study treatment will be considered as non-responders. Patients whose CDA status is unknown at the Week 5 visit for whatever reason (include early termination before Week 5 visit) will be also considered as non-responders. Only systemic CSs (as defined by medication taken orally or intravenously) are to be used to evaluate the efficacy endpoints, topical CSs will not be counted.

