 Patients who achieved CDA at or prior to the Week 5 visit and had no occurrence of daily prednis(ol)one >0.5 mg/kg before the first CDA date during the study treatment will be counted as responders.
 Two-sided 80% and 95% confidence intervals are calculated using the Exact (Clopper-Pearson) method.
 Percentages are based on the number of patients in the respective dose levels in the Analysis Population.

Source Data: Listing 16.2.4.1.1

<DIRECTORY PATH>PROGRAM NAME Executed: DDMMYYYY hh:mm

Prog note: Early treatment terminators or subjects whose CDA status are completely missing are considered non-responders.

Repeat this table for the other populations:

Table 14.2.1.2
 Proportion of Patients who Achieved Control of Disease Activity (CDA) at or Prior to Week 5 Visit without
 Prednis(ol)one >0.5 mg/kg
 mITT Population

Table 14.2.1.3
 Proportion of Patients who Achieved Control of Disease Activity (CDA) at or Prior to Week 5 Visit without
 Prednis(ol)one >0.5 mg/kg
 Per Protocol Population

Table 14.2.2.1.1
 Proportion of Patients who Achieved Control of Disease Activity (CDA) at or Prior to Week 5 Visit without Corticosteroids
 ITT Population

	400 mg (N=xx)	500 mg (N=xx)	600 mg (N=xx)	Total (N=xx)
n (%)	xx (xx.x)	xx (xx.x)	xx (xx.x)	xx (xx.x)
80% CONFIDENCE INTERVAL	(xx.x, xx.x)	(xx.x, xx.x)	(xx.x, xx.x)	(xx.x, xx.x)
95% CONFIDENCE INTERVAL	(xx.x, xx.x)	(xx.x, xx.x)	(xx.x, xx.x)	(xx.x, xx.x)

Note: Patients are classified into different dose levels according to the maximum dose they received during the 12 week treatment period.
 Control of disease activity (CDA) is defined as the time at which new lesions cease to form and established lesions begin to heal.
 Patients who achieved CDA at or before the Week 5 visit and had no occurrence of any corticosteroid before the first CDA visit during the study treatment will be counted as responders.
 Two-sided 80% and 95% confidence intervals are calculated using the Exact (Clopper-Pearson) method.
 Percentages are based on the number of patients in the respective dose levels in the Analysis Population.

Source Data: Listing 16.2.4.1.2

<DIRECTORY PATH>PROGRAM NAME Executed: DMMMMYYYY hh:mm

Prog note: Early treatment terminators or subjects whose CDA status are completely missing are considered non-responders.

Repeat this table for the other populations

Table 14.2.2.1.2
 Proportion of Patients who Achieved Control of Disease Activity (CDA) at or Prior to Week 5 Visit without Corticosteroids
 mITT Population

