3.4.6 Time from Pemphigus Diagnosis (years)

Time from event (years) = (Date of screening – First date of Pemphigus reported in Medical History + 1)/365.25

3.4.7 Control of Disease Activity (CDA), Complete Remission (CR), End of Consolidation Phase (ECP) and Relapse

Control of Disease Activity (CDA) is defined as the time at which new lesions cease to form and established lesions begin to heal. This is also considered the beginning of the consolidation phase. Date of CDA should be the first date CDA occurred i.e. a visit date or earlier date reported by the patient. If there is a relapse and a subsequent second CDA, visits from that second CDA visit forward would record the date of the second CDA. If CDA is yes, relapse must be no.

Complete remission (CR) in this study is defined as the complete healing of all lesions and absence of new lesions on any dose of corticosteroid or no steroids. Date of CR should be the first date CR occurred i.e. a visit date or earlier date reported by the patient. The duration of time in CR e.g. 8 weeks is not included in the definition. If CR is yes, CDA, ECP must be yes also, and relapse must be no.

End of Consolidation Phase (ECP) is defined as the time at which no new lesions have developed for a minimum of 2 weeks and the majority (approximately 80%) of established lesions have healed. It is at this point that most clinicians begin to taper corticosteroid doses. Date of ECP should be the first date ECP occurred i.e. a visit date or earlier date reported by the patient. If ECP is yes, CDA must be yes also, and relapse must be no.

Relapse (i.e. flare) is defined by the appearance of 3 or more new lesions in a month that do not heal spontaneously within 1 week, or by the extension of established lesions, in a patient who has achieved control of disease (i.e. CDA). Date of relapse should be the first date relapse occurred i.e. a visit date or earlier date reported by the patient. If relapse is yes, CDA, ECP and CR must be no.

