4.2 Primary Efficacy Endpoint

The primary efficacy endpoint is the proportion of patients who are able to achieve control of disease activity (CDA) within 4 weeks of starting PRN1008 treatment without the need for doses of prednis(ol)one >0.5 mg/kg on or before the Week 5 visit.

CDA is defined as the time at which new lesions cease to form and established lesions begin to heal.

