>=80 % and < 100 %	x (x.x)	x (x.x)	x (x.x)	x (x.x)
< 80%	x (x.x)	x (x.x)	x (x.x)	x (x.x)

The duration of exposure at each dose level is the date of last dose in a given dose level – date of first dose in the same dose level + 1.

The duration of exposure for “Overall” is date of last dose – date of first dose + 1.

Calculated dose in mg/day at each dose level = [Dose level (mg/day) x (Duration of exposure (x2 if BID) – doses missed)]/Duration of Exposure.

Compliance with study drug = the actual number of doses taken divided by the expected number of doses take, expressed as a percentage.

Program: <program name (date, time)>, Path: <path>

Table B.14.2.1.1.1 Proportion of patients Achieved CDA at or Prior to Week 5 without prednis(ol)one >0.5 mg/kg (mITT Population)

Achieved CDA at or Prior to Week 5 without prednis(ol)one >0.5 mg/kg	400 mg QD (N = n)	400 mg BID (N = n)	600 mg BID (N = n)	Overall (N = n)
N achieved (%)	x (x.x)	x (x.x)	x (x.x)	x (x.x)
- 80% CI	x.xx, x.xx	x.xx, x.xx	x.xx, x.xx	x.xx, x.xx
- 95% CI	x.xx, x.xx	x.xx, x.xx	x.xx, x.xx	x.xx, x.xx

Percentages are based on the number of patients in each dose group and overall.

Patients are classified into different dose levels according to the dose they received prior to achieving CDA.

Confidence Intervals are based on the Exact (Clopper-Pearson) method.

Primary efficacy endpoint: Proportion of patients who achieved CDA within 4 weeks of starting PRN1008 treatment, i.e. At or prior to Week 5, without prednis(ol)one equivalent > 0.5 mg/kg on the day prior to the assessment.

Program: <program name (date, time)>, Path: <path>

Table B.14.2.1.1.2 Proportion of patients Achieved CDA at or Prior to Week 5 without prednis(ol)one >0.5 mg/kg (Completer Population)

Table B.14.2.1.1.3 Proportion of patients Achieved CDA at or Prior to Week 5 without prednis(ol)one >0.5 mg/kg (PP Population)

Table B.14.2.1.2.1 Proportion of patients Achieved CDA at or Prior to Week 5 without prednis(ol)one >0.5 mg/kg – Subgroup – Age (mITT Population)

Subgroup	Achieved CDA at or Prior to Week 5 without prednis(ol)one >0.5 mg/kg	400 mg QD (N = n)	400 mg BID (N = n)	600 mg BID (N = n)	Overall (N = n)
Age < 50	Number of patients	n	n	n	n
	N achieved (%)	x (x.x)	x (x.x)	x (x.x)	x (x.x)
	- 80% CI	x.xx, x.xx	x.xx, x.xx	x.xx, x.xx	x.xx, x.xx
	- 95% CI	x.xx, x.xx	x.xx, x.xx	x.xx, x.xx	x.xx, x.xx
Age ≥ 50	Number of patients	n	n	n	n
	N achieved (%)	x (x.x)	x (x.x)	x (x.x)	x (x.x)

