	- 80% CI	x.xx, x.xx	x.xx, x.xx	x.xx, x.xx	x.xx, x.xx
	- 95% CI	x.xx, x.xx	x.xx, x.xx	x.xx, x.xx	x.xx, x.xx

Percentages are based on the number of patients in each subgroup, dose group and overall.

Patients are classified into different dose levels according to the dose they received prior to achieving CDA.

Confidence Intervals are based on the Exact (Clopper-Pearson) method.

Primary efficacy endpoint: Proportion of patients who achieved CDA within 4 weeks of starting PRN1008 treatment, i.e. At or prior to Week 5, without prednis(ol)one equivalent > 0.5 mg/kg on the day prior to the assessment..

Program: <program name (date, time)>, Path: <path>

Table B.14.2.1.2.2 Proportion of patients Achieved CDA at or Prior to Week 5 without prednis(ol)one >0.5 mg/kg – Subgroup – Age (Completer Population)

Table B.14.2.1.2.3 Proportion of patients Achieved CDA at or Prior to Week 5 without prednis(ol)one >0.5 mg/kg – Subgroup – Age (PP Population)

Note: Subgroups are: 'Age < 50 years' and 'Age ≥ 50 years'

Table B.14.2.1.3.1 Proportion of patients Achieved CDA at or Prior to Week 5 without prednis(ol)one >0.5 mg/kg – Subgroup – Gender (mITT Population)

Table B.14.2.1.3.2 Proportion of patients Achieved CDA at or Prior to Week 5 without prednis(ol)one >0.5 mg/kg – Subgroup – Gender (Completer Population)

Table B.14.2.1.3.3 Proportion of patients Achieved CDA at or Prior to Week 5 without prednis(ol)one >0.5 mg/kg – Subgroup – Gender (PP Population)

Note: Subgroups are: 'Male' and 'Female'

Table B.14.2.1.4.1 Proportion of patients Achieved CDA at or Prior to Week 5 without prednis(ol)one >0.5 mg/kg – Subgroup – Baseline Total AntiDSG (mITT Population)

Table B.14.2.1.4. Proportion of patients Achieved CDA at or Prior to Week 5 without prednis(ol)one >0.5 mg/kg – Subgroup – Baseline Total Anti-DSG (Completer Population)

Table B.14.2.1.4.3 Proportion of patients Achieved CDA at or Prior to Week 5 without prednis(ol)one >0.5 mg/kg – Subgroup – Baseline Total Anti-DSG (PP Population)

Note: Subgroups are: ‘Baseline Total DSG antibody \geq 100 units’ and ‘Baseline Total DSG antibody < 100 units’

Table B.14.2.1.5.1 Proportion of patients Achieved CDA at or Prior to Week 5 without prednis(ol)one >0.5 mg/kg – Subgroup – Pemphigus History (mITT Population)

Table B.14.2.1.5.2 Proportion of patients Achieved CDA at or Prior to Week 5 without prednis(ol)one >0.5 mg/kg – Subgroup – Pemphigus History (Completer Population)

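### The Part B SAP applies the primary endpoint's 0.5 mg/kg steroid limit over incompatible windows: up to Week 5 in 4.2, but a single day in 5.4.1 and the table footnotes

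*SAP*

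**What the plan says.** The primary efficacy endpoint is stated in several places, and the steroid limit is worded differently in each.

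- Protocol 11.1.2: CDA "within 4 weeks of starting PRN1008 treatment without the need for doses of prednis(ol)one > 0.5 mg/kg". No window for the steroid limit is named.
- Part B SAP 4.2: CDA within 4 weeks "without the need for doses of prednis(ol)one >0.5 mg/kg on or before the Week 5 visit".
- Part B SAP 5.4.1, the operational rule: patients reaching CDA by Week 5 "without prednis(ol)one >0.5 mg/kg on the date prior to the CDA will be considered as responders". Non-responders are defined by the same single day. The section adds that higher doses after first CDA do not change the status.
- Part B shells, footnote to primary Table B.14.2.1.1.1: "At or prior to Week 5, without prednis(ol)one equivalent > 0.5 mg/kg on the day prior to the assessment". The subgroup Table B.14.2.1.2.1 has the same condition, "without prednis(ol)one equivalent > 0.5 mg/kg on the day prior to the assessment".
- Part B SAP 3.4.7, on dating CDA: "Date of CDA should be the first date CDA occurred i.e. a visit date or earlier date reported by the patient".
- Part A SAP 8.1: patients who reach CDA and "have no occurrence of daily prednis(ol)one >0.5 mg/kg before the date of the first CDA will be considered as responders". The footnote to Part A Table 14.2.1.1 agrees: "had no occurrence of daily prednis(ol)one >0.5 mg/kg before the first CDA date during the study treatment will be counted as responders". Part A SAP 3.2.2 and the footnote to Part A Listing 16.2.4.1.1 instead extend the limit to the Week 5 visit.

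Part B SAP 4.7, the list of changes from the protocol, does not mention the steroid rule for the primary endpoint.

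**The concern.** The endpoint is meant to credit PRN1008 with disease control reached without high-dose steroid. A one-day check does not establish that. A patient who was given 1.0 mg/kg and was at or below 0.5 mg/kg on the one day examined would be tabulated as having responded without such a dose.

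The Part B SAP also gives three answers to one question, and nothing in it ranks or reconciles them. A programmer would probably follow 5.4.1, but it would remain open whether the reported CDA date or the visit date fixes the day. What is at stake is the classification of individual patients on the primary endpoint. Comparability with Part A is also at stake, because protocol 11.5.3 and 11.9.1 allow data from the two Parts to be combined.

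**Working it through.** **1. The windows side by side.** Two patient types separate them.

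- Type 1: CDA on Day 15 on no or low steroid, then 1.0 mg/kg from Day 20.
- Type 2: above 0.5 mg/kg on an earlier day, but at or below 0.5 mg/kg on the day before CDA. For example: 1.0 mg/kg on Days 15–21, 0.5 mg/kg on Days 22–28, CDA dated at the Day 29 visit.

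| Rule | Days examined | Type 1 | Type 2 |
|---|---|---|---|
| Part B 4.2 | every day to the Week 5 visit | non-responder | non-responder |
| Part B 5.4.1 | day before CDA | responder | responder |
| Part B table footnotes | day before the assessment | responder | responder in this example |
| Part A 8.1 | every day before first CDA | responder | non-responder |

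The footnote entries assume that CDA is dated at the visit. Where CDA is back-dated under 3.4.7, the day before CDA and the day before the assessment are different days.

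**2. Direction.** CDA must occur by the Week 5 visit, so both single days lie inside the 4.2 window. Anyone who fails a one-day check also fails 4.2, so against 4.2 the one-day checks can only add responders. Against Part A 8.1, the 5.4.1 check can also only add responders, because the day before CDA lies inside that window. The footnote day can fall on or after a back-dated CDA, so against Part A 8.1 it can move a patient either way.

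**3. How a patient could get there.** Protocol exclusion criterion 6 bars more than 0.5 mg/kg in the two weeks before Day 1. In Appendix 1B, rescue #1 stops PRN1008 and rescue #3 applies only after failure by 4 weeks. That leaves rescue #2, which gives 1.0 mg/kg with PRN1008 continued.

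- Type 1 needs no taper at all.
- Type 2 needs a reduction faster than Appendix 7 recommends. That percentage method first holds the dose for two weeks after disease control, then cuts 15% every three weeks: 0.85^4 = 0.52 and 0.85^5 = 0.44, so five steps, or 15 weeks, from 1.0 to below 0.5 mg/kg. The alternative table takes four weekly steps from 40 to 20 mg. Appendix 1B leaves tapering to clinical discretion, so a quicker reduction is possible. In the example it implies an unscheduled review near Day 22, because scheduled visits fall on Days 15 and 29.

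**4. Size of one reclassified patient.** The plan's own precision figure reproduces: at 50% and n = 25, 1.2816 × √(0.25/25) = 0.128, the stated ±13%. That is the normal approximation, whereas the analysis uses Clopper-Pearson intervals. The mITT N is not given, so 15 to 25 is assumed.

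| N | One patient | Example, exact 80% CI | Half-width | Ratio |
|---|---|---|---|---|
| 25 | 4.0 points | 12/25 = 48.0% (33.8–62.5) to 13/25 = 52.0% (37.5–66.2) | 14.4 | 0.28 |
| 20 | 5.0 points | 10/20 = 50.0% (33.8–66.2) to 11/20 = 55.0% (38.5–70.7) | 16.2 | 0.31 |
| 15 | 6.7 points | 7/15 = 46.7% (28.2–65.8) to 8/15 = 53.3% (34.2–71.8) | 18.8 | 0.35 |

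How many patients are of either type cannot be derived from the documents. Protocol 1.4.2.1 reports two patients with temporary high-dose steroid among the first 21 treated, without its timing relative to CDA or Week 5.

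**The case against.** The best defence is that 5.4.1 is explicit. It presents itself as the operational definition and deals directly with later high doses. The shells are described as defining layout and open to adjustment, so their footnotes are weak evidence of a rival rule. This SAP covers Part B only, its analysis is descriptive (3.8), and individual steroid doses are listed and plotted. Under the recommended taper, a patient rescued at Day 15 would still be above 0.5 mg/kg on Day 28, and every rule would then agree.

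Much of this stands, and it limits the size of the problem. It does not remove it. Section 4.2 is also explicit, and its conflict with 5.4.1 over doses given after CDA does not depend on any taper. Listings let a reader rebuild the classification but do not say which one is primary.

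A reader might infer that Part A supplies a clean standard from which Part B departed. The documents do not support that: Part A 3.2.2 and Listing 16.2.4.1.1 run to Week 5, while Part A 8.1 stops at first CDA. Part A has a similar split. What is particular to Part B is the one-day check, which no Part A text uses for the primary endpoint.

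**Conclusion.** The inconsistency is real and should be corrected. Part B SAP 4.2, 5.4.1 and the primary table footnotes can classify the same patient differently, and relative to 4.2 the one-day rules err only towards response. The practical effect is probably small and may be nil: 4.0 points per patient at N = 25, an unknown and possibly zero number of patients, and no hypothesis test.

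Two stronger readings should be resisted. One is that 5.4.1 contradicts the protocol. Protocol 11.1.2 names no steroid window, so the most that can be said is that a one-day check fits poorly with the ordinary sense of not needing such doses. The other is that the Part B response rate is materially inflated. No count supports this, and type 2 patients require a reduction quicker than the recommended taper, so they are probably rare.

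The conclusion rests on the texts as written. The per-patient figures assume an N of 15 to 25.

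**What to change.** Choose one cumulative window for systemic prednis(ol)one-equivalent above 0.5 mg/kg and write it identically in Part B SAP 4.2, 5.4.1 and the footnotes to Tables B.14.2.1.1.1 and B.14.2.1.2.1. Either choice is workable:

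- any day from first PRN1008 dose to the day before first CDA, matching Part A 8.1, with 4.2 amended; or
- any day up to the Week 5 visit, matching 4.2, with 5.4.1 amended.

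In addition:

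- State whether the reported CDA date or the visit date applies.
- Report the day-before rule only as a labelled sensitivity analysis.
- Record the operational rule in 4.7.
- State the window for the with/without steroid endpoints in 5.4.2.1, which names none; 5.4.2.4 and Listing B.16.2.6.10 only suggest a day-before convention.
- If Parts A and B are combined, derive both with the same window.

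The cost is SAP wording and a revised derivation from steroid records already collected. The response rate may come out slightly lower.

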5.4.1.1 Subset Analyses

The robustness of the primary endpoint results will be explored by calculating the number and percent of patients meeting the primary efficacy endpoint overall (i.e. across all doses) within the following patient subsets:

- 1) Age (< 50 years, ≥ 50 years)
- 2) Gender
- 3) Total anti-desmoglein (DSG) antibody (≥ 100, < 100 units) at baseline.
- 4) Pemphigus History Type: Newly diagnosed (≤ 6 months from screening) vs. relapsed (> 6 months from screening)
- 5) Pemphigus anti-DSG Profile at baseline: Pemphigus Vulgaris (PV) vs. Pemphigus foliaceus (PF) vs. negative anti-DSG profile, defined as follows:
 - PV: anti-DSG3 positive with anti-DSG1 negative or anti-DSG3 positive with anti-DSG1 positive.
 - PF: anti-DSG1 positive only
 - Negative anti-DSG profile: neither detectable.
- 6) Pemphigus Severity: PDAI < 15 (mild-moderate) vs PDAI ≥ 15 (moderate-severe) at baseline If screening PDAI is not available use Week 1 Day 1 Pre-dose.

A sensitivity analysis using the Completer and PP populations will be provided for each subset analysis.

5.4.2 Secondary Efficacy Endpoints

5.4.2.1 CDA Responses

The number and percentage of patients who meet the criteria below will be tabulated by dose level and overall where the response first occurred and overall. 80% and 95% CIs will be calculated for the proportions using the Exact (Clopper-Pearson) method .

- 1) Cumulative incidence of patients able to achieve CDA by each visit
- 2) Cumulative incidence of patients able to achieve CDA by each visit on zero steroids.
- 3) Cumulative incidence of patients able to achieve CDA by each visit **with** the need for doses of prednis(ol)one of greater than 0.5 mg/kg
- 4) Cumulative incidence of patients able to achieve CDA by each visit **without** the need for doses of prednis(ol)one of greater than 0.5 mg/kg
- 5) Proportion of patients able to achieve CDA at each visit
- 6) Proportion of patients able to achieve CDA at each visit **with** the need for doses of prednis(ol)one of greater than 0.5 mg/kg
- 7) Proportion of patients able to achieve CDA at each visit **without** the need for doses of prednis(ol)one of greater than 0.5 mg/kg
- 8) Cumulative incidence of patients able to achieve CR by each visit
- 9) Cumulative incidence of patients able to achieve CR by each visit **with** the need for doses of prednis(ol)one of greater than 0.5 mg/kg
- 10) Cumulative incidence of patients able to achieve CR by each visit **without** the need for doses of prednis(ol)one of greater than 0.5 mg/kg
- 11) Proportion of patients able to achieve CR at each visit
- 12) Proportion of patients able to achieve CR at each visit **with** the need for doses of prednis(ol)one of greater than 0.5 mg/kg
- 13) Proportion of patients able to achieve CR at each visit **without** the need for doses of prednis(ol)one of greater than 0.5 mg/kg
- 14) Proportion of patients able to achieve a complete CR **with** the need for dose of prednis(ol)one of greater than 0.5 mg/kg within 24 weeks, i.e. on or prior to Week 25 visit
- 15) Proportion of patients able to achieve a complete response (CR) **without** prednis(ol)one of greater than 0.5 mg/kg within 24 weeks, i.e. on or prior to Week 25 visit

The CDA status, CR status, ECP status, and Relapse status by visit, by patient will be presented in a listing.

Duration of CR will be summarized and listed, and is defined by the longest period of consecutive visits in CR (last known CR date – first known CR date + 1). Each subject will only have one CR duration as a result.

A sensitivity analysis using the Completer and PP populations will be provided for all analyses of CDA response.

